**Vapotherm, Inc**  
**Hypercapnia Stabilization RCT NIPPV v HVNI**  
**Confidential**

**Glossary of Definitions and Terms**

**High Flow Nasal Cannula (HFNC):** Nasal cannula system that delivers flow rates of respiratory gas meeting or exceeding a patient's normal spontaneous inspiratory flow demand. HFNC systems must maintain adequate heating and humidification of the delivered gas to protect the airway tissues from dryness.

**High Velocity Nasal Insufflation (HVNI):** HVNI exists as a refined form of HFNC, a system consisting of heated and humidified gas mixtures of varying FiO2 delivered to a patient using a small-bore nasal cannula, at generally high flow rates imparted with increased velocity as compared to other standard large-bore cannulae. The flow rates of respiratory gas generally exceed a patient's normal spontaneous inspiratory flow demand. HVNI systems must maintain adequate heating and humidification of the delivered gas to protect the nasal tissues from dryness and provide patient comfort.

**Non-Invasive Positive Pressure Ventilation (NIPPV):** Breathing assist where a mask is strapped tightly to a patient's face and bi-level positive airway pressure is administered at an established frequency to support patient ventilation. NIPPV may also refer to Continuous Positive Airway Pressure (CPAP).

**Intubation:** The placement of an endotracheal tube to facilitate respiratory support and provide airway protection.

**Respiratory Failure:** The inability to maintain sufficient arterial blood oxygen saturation and/or retention of carbon dioxide levels during unassisted spontaneous breathing.

**Pulse Oximetry Reading (SpO2):** Indirect measure of a patient's arterial blood oxygen saturation using pulse oximetry technology that utilizes oxygen/hemoglobin concentrations.

**Resting SpO2:** SpO2 value the patient demonstrated at rest, while sitting upright and connected to the pulse oximetry monitor prior to the start of the study session. This value will be patient specific and reflect oxygen saturation.

**Desaturation SpO2:** The SpO2 value considered to be the point of desaturation where the value drops below a specified threshold. This value is based on the desaturation requirement for reimbursement of oxygen therapy.

**Ventilatory Work Effort / Work of Breathing (WOB):** The physical, physiologic muscular demands of breathing manifested through signs and symptoms of increased physical exertion, manifested through pulmonary changes leading to the use of accessory muscles for inspiration or exhalation.

**Fraction of inspired oxygen (FiO2%):** The percent of the delivered respiratory gas mixture that is oxygen, expressed as a fraction.

**Ventilatory Rate (Respiratory Rate; RR, BPM):** The number of breaths a patient takes per minute (breaths·min).

**Blood Pressure (BP):** as measured by systolic and diastolic pressures of the blood contained in the circulatory system, measured for this study in mmHg.

**Vapotherm, Inc**  
**Hypercapnia Stabilization RCT NIPPV v HVNI**  
**Confidential**

Heart Rate (HR): The number of heart beats per minute (beats·min).

Modified Borg Scale (Borg): Dyspnea is an important measure of patient respiratory distress & pulmonary functional status. The rate of perceived dyspnea (RPD), an accepted and well-published form of measuring breathlessness, is determined by patients and clinicians to using specific descriptors, on a scale of 0 (no dyspnea) to 10 (unbearable dyspnea).

Standard of Care (SOC): Site standard practices for the medical care of patients presenting with specific symptoms.

Case Report Form (CRF): The form used to record pertinent patient data to address the study aim(s). CRFs do not contain patient names or medical record numbers; rather they will be coded with a patient number and the site principal investigator at each center will maintain the key. CRFs may be digitally compiled. The CRFs are the property of Vapotherm.

# Vapotherm, Inc

## Hypercapnia Stabilization RCT NIPPV v HVNI

Confidential

### I. Background and Significance

Patients with Chronic Obstructive Pulmonary Disease experience a complex physiologic derangement marked by various levels of chronic increased mucus production and chronic alveolar destruction. Ultimately, this leads to impaired ventilation and difficulties with gas exchange, producing hypercapnia, and in some cases leading to hypoxia. While the chronic disease typically progresses gradually over many years, patients experience several intermittent rapid decompensations per year, in the form of acute exacerbations. The etiology of these acute exacerbations is multi-factorial, but they are often hallmark by increased work of breathing, discomfort/shortness of breath, and the more severe exacerbations progress to hypercapnic respiratory acidosis, hypoxia, and ultimately respiratory failure.

Treatment of acute exacerbations of COPD is multimodal; these modalities often include bronchodilators, steroids, and antibiotics. Respiratory support and treatment of acute hypercapnic respiratory failure (AHRF) secondary to an Acute Exacerbation of Chronic Obstructive Pulmonary Disease (AECOPD) is most commonly provided through non-invasive positive pressure ventilation (NIPPV), or in some cases mechanical ventilation (MV). A recent Cochrane meta-analysis by Osadnik et al 2017 compared the efficacy of NIPPV when applied in conjunction with usual care practices versus usual care without MV in adults with AHRF secondary to AECOPD. Data from 17 randomized controlled trials containing 1264 patients, this Cochrane meta-analysis demonstrated that NIPPV decreased the risk of mortality by 46% and decreased risk of requiring intubation by 65%, which resulted in an associated reduction in hospital LOS, reduced incidence of complications, and improvement in pH & PaO2 within 1-hour. The improvement in PaCO2 was shown to trend but was not found to be statistically significant. Further *post hoc* analysis showed a positive statistical result. The authors concluded that NIPPV is “beneficial as a first-line intervention in conjunction with usual care for reducing the likelihood of mortality and intubation in patients admitted with AHRF secondary to AECOPD,” and the benefits “appear similar for patients with mild acidosis (pH 7.30 to 7.35) versus a more severe nature (pH < 7.30), and when NIV is applied within the intensive care unit (ICU) or ward setting.”

Ventilatory therapy has historically been delivered via various devices that provide positive pressure (MV, NIPPV, and continuous positive airway pressure [CPAP]). The goal of using these devices is to have an effect on the volume component of the alveolar ventilation equation: Alveolar ventilation = (Volume-Dead Space) X Respiratory Rate. Flow-based therapy, particularly High-Velocity Nasal Insufflation [HVNI], supports oxygenation and ventilation by flushing the dead space component of the alveolar ventilation equation. Furthermore, it has been demonstrated that NIPPV & HVNI provide comparable therapeutic support. Two separate mechanisms of action are available which influence alveolar ventilation. HVNI has been shown to be a therapeutic alternative to NIPPV.

Vapotherm HVNI therapy, is premised on the technical ability to create ideally conditioned medical grade vapor, which is delivered nasally with an intent to support spontaneous ventilation. Vapotherm technology is unique in its ability to provide this optimally conditioned gas through a small-prong nasal cannula resulting in a high velocity, physiologically warmed humidified gas without the well-known adverse effects related to drying and cooling of the nasal mucosa that occurs with simple oxygen therapy. In addition and uniquely, the high velocity nasal flow facilitates a well described mechanism of improving ventilatory efficiency by way of eliminating carbon dioxide traditionally stacked in anatomical dead space of the upper airway. Upper airway purge is important to alveolar gas exchange as the gas that is drawn to the respiratory regions of the lungs comes from the dead space or anatomical reservoir created by the flush. This mechanism operates similarly to that of oxygen conservation masks (re-breathers). These masks create an

# Vapotherm, Inc

## Hypercapnia Stabilization RCT NIPPV v HVNI

Confidential

artificial reservoir through bags to reduce the bulk flow requirements from the oxygen source to achieve the same oxygenation effect. HVNI uses the anatomic dead space as a natural reservoir for oxygen to support patients who require oxygenation when needed as well as utilize anatomic dead space to flush CO2 from the respiratory stack. Based on mathematical modeling of standard anatomy, physiologic studies and clinical observations, a flow rate of 4 to 8 L·min through Vapotherm's neonatal cannulae, or 25 to 40 L·min through Vapotherm's adult cannulae, would purge the anatomical reservoir of the upper airway of CO2 in the window of time between breaths.

Vapotherm's humidification system is specifically designed to tolerate a high back pressure in the humidification cartridge that is generated by passing these high flow rates through small bore cannulae that result in the appropriate flow velocities (turbulent energy). Since 2000, Vapotherm HVNI has been used extensively and has been well studied and the clinical impact of this ventilation effect using Vapotherm's conventional cannula line is well described. A multi-center randomized clinical trial also demonstrated the noninferiority of HVNI to NIPPV in the treatment of undifferentiated respiratory distress for patients presenting to the Emergency Department. The current study is an extension of the prior published studies' outcomes. The goal of this randomized control trial is to evaluate, the relative efficacy of HVNI or NIPPV to clinically stabilize & relieve the patient's moderate-to-severe hypercapnic respiratory distress, through oxygenation and ventilation, upon presentation.

**Vapotherm, Inc**  
**Hypercapnia Stabilization RCT NIPPV v HVNI**  
**Confidential**

## II. Overall Study Objective

The **overall objective** of this randomized study is to evaluate the efficacy of HVNI, in comparison to NIPPV, to clinically stabilize and provide respiratory therapy to patients who have COPD with moderate-to-severe hypercapnic respiratory distress upon presentation.

The **hypothesis**: HVNI is comparable to NIPPV in the stabilization and relief of moderate-to-severe hypercapnic respiratory distress upon presentation, by relieving the patient's dyspnea (breathlessness) within 4 hours to a comparable degree to NIPPV.

$$H_0: \mu_T \leq \mu_C - 1$$

$$H_a: \mu_T > \mu_C - 1,$$

where  $\mu_T$  and  $\mu_C$  are the improvement in modified BORG at 4 hours for treatment (Vapotherm) and control (NIPPV), respectively, and the non-inferiority margin is 1.

To test this hypothesis, the study will be conducted with the following specific aims:

**Aim #1: Primary Outcome.** The primary endpoint is to evaluate the patient's relief of dyspnea, as measured by the modified Borg, rated perceived dyspnea [RPD 0-10], during the 4-hour post-therapy initiation interval. These measurements will be compiled over the time course of the study – baseline, 30min, 1h, and 4h.

**Aim #2: Secondary Outcomes.** The secondary endpoints evaluate treatment failure (need for intubation), indices of Work of Breathing (patient vitals [HR, RR, SpO2]), patient's clinical stability during hypercapnic respiratory distress, as measured by an index of patient communication capability [Patient Stability Index: 0-10], venous blood gases (pH, PCO2, PO2, bicarbonate, base excess), basic metabolic panel\* (lactate, Na+, K+, Cl, glucose), and patient disposition (length of stay [LOS]). These measurements will be compiled over the time course of the study – baseline\*, 30min, 1h, and 4h. The Patient Stability Index is described in the protocol.

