### III. Subject Selection

Patients will be identified and recruited by study investigators or research staff trained on this particular trial. The study will initiate in an Emergency Department setting, or from an inpatient setting, and transfer to an acute-care unit that is sufficiently staffed and skilled in NIPPV and HVNI to support patients presenting with moderate to severe hypercapnic respiratory acidosis. Testing during this study will be performed in the presence of health care individuals who will provide appropriate supervision and staff training to maintain patient safety. The test will evaluate the patient's relief of dyspnea, clinical stability, WOB indices (vitals, RPD, ventilation, oxygenation), patient disposition, and patient and physician perceptions for each study arm before and during therapy for hypercapnic respiratory distress. Initial patient contact will be made by study investigators or research staff trained on this particular trial. Participants may or may not decide to enroll after being consented. Consent in this ED/acute-care-setting-based study will be obtained by a verbal consent prior to participation/randomization followed by written consent (when patient is medically stable), or a written consent prior to participation/randomization. The verbal consent will be obtained and documented in the patient chart along with a witnessed attestation. The written consent will be obtained once patient is able to participate in a consent discussion, when their respiratory symptoms are manageable.

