# Vapotherm, Inc

## Hypercapnia Stabilization RCT NIPPV v HVNI

Confidential

target should be to lower respiratory rate by 20% or below 24 br/min, while subsequently clinically stabilizing and reliving moderate-to-severe hypercapnic respiratory distress.

***HVNI will be initiated per the settings identified here***, after which settings will be titrated per standard practice for optimal effect. Patients will be fitted with a Vapotherm nasal cannula that will be applied by a respiratory therapist or other clinician skilled in management of HVNI (not to exceed 50% occlusion of the nares). When appropriate cannula are placed, the HVNI initial settings will be the following:  $\text{FiO}_2 = 0.50$  (unless the patient is receiving supplemental  $\text{O}_2$ , and then  $\text{FiO}_2$  will reflect amount of  $\text{O}_2$  patient is receiving provided that the  $\text{SpO}_2$  monitor reflects sufficient oxygenation), Flow = 30 L/min, and Temperature = 37°C. The flowrate can be decreased/increased as rapidly as necessary to optimize patient response and comfort, after a 5min acclimatization. Starting temperature will be 37°C; if patients find the gas temperature to be uncomfortable (warm), it can be lowered as necessary down to 33°C to enhance tolerance. The  $\text{FiO}_2$  will be set initially to approximate the likely previous dosage (if any) to initially to assure adequate oxygenation, but this should be adjusted (range 0.21 to 1.0) to maintain an  $\text{SpO}_2$  88-94%, per normal clinical management. If possible,  $\text{FiO}_2$  should be weaned to 0.30 or lower while maintaining  $\text{SpO}_2$  88-94%. NOTE: The flow rate is expected to be increased to the maximum rate of 40 L/min before a patient is removed from HVNI therapy.

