***NIPPV will be initiated per the initial settings identified here***, after which settings will be titrated per standard practice for optimal effect. When patients are placed, the NIPPV initial settings will be the following: 12 cmH2O / 6 cmH2O (IPAP/EPAP), such that IPAP is 6 cmH2O above EPAP, with Backup Ventilation Rate = 0-4 breathes/min (lowest), and applied at the site's standard of care (SOC) for humidification (settings to be recorded). Patients will be fit with an oronasal mask using a fitting gauge that will be applied by a respiratory therapist or other clinician skilled in management of NIPPV. Initial pressures will be at low end of suggested range but can be increased as rapidly as necessary to alleviate respiratory distress. Targeted tidal volumes of 6-8 ml/kg ideal body weight will be the volume goal. If patients find pressures uncomfortably high/low, they can be adjusted as necessary by 1 to 2 cmH2O decrements to enhance tolerance. EPAP (PEEP) can also be adjusted upward as needed to reduce triggering effort (by counterbalancing auto-PEEP) or to improve oxygenation.  $\text{FiO}_2$  will be 0.50 initially to assure adequate oxygenation (unless the patient is receiving supplemental  $\text{O}_2$ , and then  $\text{FiO}_2$  will reflect amount of  $\text{O}_2$  patient is receiving provided that the  $\text{SpO}_2$  monitor reflects sufficient oxygenation), but should be adjusted promptly to maintain an  $\text{SpO}_2$  88-94%, per normal clinical management. If possible,  $\text{FiO}_2$  should be weaned to 0.30 or lower while maintaining  $\text{SpO}_2$  88-94%.

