#### **Phase 3 – Therapy Evaluation Interval #1**

The Therapy Evaluation Interval 1 at 30-minutes will be used to perform a VBG draw for all patients to determine if patients need emergent intubation or if Flow/FiO2 or IPAP/EPAP/FiO2 settings should be adjusted.

At the 30-minutes post-initiation of randomized therapy (HVNI or NIPPV), the patient will be evaluated. Patient Stability Index evaluation will be evaluated by clinicians and recorded at this time. At 30-minutes post initiation of randomized therapy, a venous blood gas sample will be drawn to establish the patient status. Patient status for physiologic parameters (RR, HR, SpO2, BP, RPD) and venous blood gas parameters (PO2, PCO2, pH, bicarbonate, base excess ) will also be collected at this time. For the RPD, the clinician will record patient scores. For VAS, at this time, only patient assessment scores will take place.

Any changes in the assigned therapy settings will be recorded at this interval. Record any relevant treatment intolerance and failure, need for endotracheal intubation, time spent under positive-pressure ventilation , patient mortality, elevation of patient status, and transfer to other inpatient ward/units. Should the patient be placed on intubation prior to this therapy evaluation interval, the physiologic parameters and venous blood gas parameters will be subsequently collected at intubation time. Should the patient be designated by attending clinician for discharge from the ED prior to this therapy evaluation interval, the physiologic parameters, venous blood gas parameters, and final assessment scores (per Phase 6) will be subsequently collected at this time.

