**Vapotherm, Inc**  
**Hypercapnia Stabilization RCT NIPPV v HVNI**  
**Confidential**

## VII. Data Collection

**Table 1. Key study data and collection points for each Phase of the Study.**

	Study Start	Baseline Characterization	Therapy @ 30 minutes	Therapy @ 1hr	Therapy @ 4hr	@ Study End
Patient History & Health Profile	X					X
Treatment: Flow & O2	X	X	X	X	X	X
Patient Stability Index		X	X	X	X	
Physiologic Parameters	X	X	X	X	X	
Blood Gas Parameters		X	X	X	X	
Clinician Perception Scores		X			X	X
Patient Perception Scores		X	X	X	X	X

Patient enrollment data collection will include patient history, health, demographics, and current respiratory therapies. Patient data will also include COVID-19 status. Only Phase 1, study start, will record the patient history and background information. All data collection will be noted with date/time as possible by the clinicians and per the SOC or available medical records. Blood samples (VBG) will be drawn within +15/-15 min of the indicated time from therapy initiation. Vital signs and indices will be recorded within +5/-5 of the indicated time from therapy initiation. Vital signs, including heart rate (HR), respiratory rate (RR) and blood oxygen saturation by pulse oximetry (SpO2), will be reported from the patient monitoring systems in use. If patient is intubated this date and time, blood gases, and physiologic parameters will be recorded in addition to the reason for intubation, as deemed by the clinician(s).

For each phase, the following data will be recorded for comparison:

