### Physiologic Parameters

- Rated Perceived Dyspnea (RPD), SpO2, HR, RR, BP

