### Secondary Endpoints

- Physiologic parameters –SpO2, HR, RR, BP,
- Secondary Blood Gas parameters – Changes in venous PCO2, venous PO2, venous pH, venous bicarbonate, venous base excess
- Patient Stability Index – continuous VAS score on a scale from unable to speak, due to severe respiratory distress, up to speaks in full sentences without severe respiratory distress.

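### Both arms adjust FiO2 to hold SpO2 at 88-94%, so once titrated the SpO2 secondary endpoint says little about oxygenation; SpO2/FiO2 and set FiO2 should be added beside it

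*Combined protocol and SAP*

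**What the plan says.** **Endpoint.** Section II, Aim #2 lists SpO2 with heart rate and respiratory rate under the "indices of Work of Breathing (patient vitals [HR, RR, SpO 2", measured at baseline, 30 min, 1 h and 4 h. The Secondary Endpoints list in Section VII has "Physiologic parameters –SpO 2 , HR, RR, BP". Section III describes the scope of these measures as "WOB indices (vitals, RPD, ventilation, oxygenation", so oxygenation is part of what they are meant to show. Section II closes by saying that the endpoints are to establish that HVNI is comparable to NIPPV.

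**Titration.** In Section VI (Initial Settings), both arms start at FiO2 0.50, or at the patient's current oxygen if saturation is sufficient. On HVNI, FiO2 approximates any previous dosage, "but this should be adjusted (range 0.21 to 1.0) to maintain an" SpO2 of 88-94%. On NIPPV, FiO2 starts as above, "but should be adjusted promptly to maintain an" SpO2 in the same band. Both arms are to wean FiO2 to 0.30 or lower, where possible, within that band.

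**Recording.** The Table 1 row "Treatment: Flow & O2" is marked at all six points. The physiologic set ("Rated Perceived Dyspnea (RPD), SpO 2 , HR, RR, BP") is marked from study start to 4 h. At 30 min, 1 h and 4 h, "Any changes in the assigned therapy settings will be recorded at this interval".

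**Analysis.** Section VIII compares patient parameters by arm and time with repeated-measures ANOVA at p < 0.05. It makes no allowance for FiO2, and no endpoint is built on FiO2 or SpO2/FiO2.

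**The concern.** SpO2 is the quantity that staff are steering, and FiO2 is the lever. If both arms are steered to one band, a device that oxygenates less well is compensated by more oxygen. The difference then leaves SpO2 and moves into FiO2, which is recorded but not compared.

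Raw SpO2 also has no clear better direction here. A patient above 94% on the starting FiO2 who is weaned as instructed shows a falling SpO2 although the protocol was followed.

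At stake is the reading of a secondary result. This is a non-inferiority trial whose endpoints are meant to support comparability, and similar SpO2 is what the titration rule tends to produce whether or not the devices oxygenate equally well.

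**Working it through.** **1. Is there a planned figure to reproduce?** Not for SpO2: the plan gives no SD, power or expected difference for it. The primary sample size (Section V) is needed here only for the arm size. Taking the assumed 0.9 difference as favouring HVNI, as the table there shows:
- Pooled variance = (2.4² + 2.9²)/2 = 7.085, so SD = 2.662.
- n per arm = 2 × (1.960 + 0.842)² × 7.085 / (1.0 + 0.9)² = 30.8, or 31 by the normal approximation.
- With the t distribution, 32 per arm gives 80.3% power. Enrolment is 64/0.80 = 80.

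The stated 64 evaluable and 80 enrolled reproduce, and nothing below alters them.

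**2. Arithmetic inside the band.** If every patient is in the band, arm means can differ by at most 94 − 88 = 6 points. At SpO2 91%, SpO2/FiO2 is:

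| FiO2 | Ratio |
|---|---|
| 0.21 | 433 |
| 0.30 | 303 |
| 0.40 | 228 |
| 0.50 | 182 |
| 1.0 | 91 |

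From 0.30 to 0.40 the ratio falls by 1 − 227.5/303.3 = 25%, while SpO2 differs by 0. These FiO2 values are chosen for illustration; the documents give no FiO2 distribution.

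**3. How far does this depend on complete titration?** A simulation with 32 per arm, 3,000 repetitions and a two-sided 0.05 t-test at one time point. The inputs are assumptions, not from the documents:
- FiO2 needed for SpO2 91%: median 0.35, SD 0.35 on the log scale, multiplied by a factor in the HVNI arm.
- Set FiO2 moves from 0.50 towards the need by the stated degree (log scale), limited to 0.21-1.0.
- SpO2 = 91 + 8 × ln(set FiO2/need) + noise with SD 1.5.
- The degree of titration is the same in both arms.

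Power, SpO2 / SpO2-FiO2 ratio:

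| Titration | Need ×1.2 | Need ×1.3 | Need ×1.5 |
|---|---|---|---|
| None | 45% / 45% | 76% / 76% | 97% / 97% |
| 50% | 29% / 52% | 54% / 84% | 87% / 99% |
| 80% | 11% / 52% | 19% / 83% | 37% / >99% |
| Full | 6% / 53% | 6% / 83% | 6% / >99% |

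With full titration, SpO2 detects little more than the 5% false-positive rate. For a 1.3-fold need the mean difference is −0.08 SpO2 points, against −59 in the ratio. With no difference in need, both tests reject in about 4% to 5% of repetitions.

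**4. Do other planned measures fill the gap?** Only in part. Section VI defines failure to oxygenate, and one intubation-reason category covers not holding saturation above 88% at FiO2 1.0. Both register only patients failing on full oxygen. Venous PO2 is a secondary endpoint but is neither an arterial nor an SpO2-based index. None would register one arm at 0.40 against the other at 0.30.

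**The case against.** **SpO2 is not fixed by the protocol.** A reader might infer that it cannot show any difference. The documents do not support that. Patients start at 0.50 or at their current oxygen, adjustment follows normal clinical management, and weaning is only where possible. SpO2 can differ at 30 min or 1 h, before titration is complete, or in patients who miss the target at FiO2 1.0. The 6-point ceiling assumes everyone is in the band, and at 50% titration the simulation still gives SpO2 54% power for a 1.3-fold need. This stands: the claim is weak information once titrated, not none.

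**The ratio is also in staff hands.** The trial is unblinded and FiO2 is what staff set. Two readings inside the band give 94/0.50 = 188 and 88/0.30 = 293, so slower weaning in one arm would look like worse oxygenation. The simulation does not test this, because it titrates both arms alike. The ratio also uses set rather than delivered FiO2, across a nasal cannula and a fitted mask, and ignores flow and EPAP, although Section VI allows EPAP to be raised for oxygenation. This stands too. It argues for adding the ratio as supportive, not for substituting it for SpO2.

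**The data are not quite in hand.** Table 1 does not name set FiO2, and no rule ties the recorded setting to the time of the SpO2 reading. A reader might take the initial-settings text as already supplying a baseline FiO2. It describes the device setting at the start of therapy, whereas baseline is measured before therapy.

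**It is one of many secondary items.** Aim #2 files SpO2 under work of breathing, and the hypothesis concerns dyspnea. True, but Section III includes oxygenation in those indices.

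**Conclusion.** The point holds as a cheap improvement to a secondary endpoint. Under the plan's own titration rule, raw SpO2 is weakly informative about oxygenation once titration is complete, most of all at 4 h, and similar values would not show comparable oxygenation. The 25% fall in the ratio at equal SpO2 is exact arithmetic on illustrative FiO2 values. It is not a forecast of a difference between the arms, nor proof that a patient needing 0.40 is 25% worse. The power figures rest on the assumptions listed and on equal titration behaviour in the two arms.

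A reader might also infer that the non-inferiority conclusion is at risk, or that the plan has no FiO2-conditioned outcome at all. Neither follows. The primary endpoint is the modified Borg score, and its analysis and sample size are untouched. Failure to oxygenate is defined, but captures only severe failure.

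**What to change.** - In Section II (Aim #2) and the Section VII endpoint list, add SpO2/FiO2 and set FiO2 at 30 min, 1 h and 4 h as the secondary oxygenation measures, using the set FiO2 recorded at the time of each SpO2 reading.
- Keep reporting raw SpO2, interpreted as adherence to the target. Also report the share of patients at FiO2 0.30 or lower, a goal that Section VI already names.
- Make the oxygen item in Table 1 and on the case report form name set FiO2.
- For a baseline ratio in patients on low-flow oxygen, state the conversion rule, or omit the baseline ratio.
- In Section VIII, label the ratio supportive and state its limits: unblinded titration and weaning, set rather than delivered FiO2, and no account of flow or EPAP.

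The cost is endpoint wording, one derived variable, and a clearer, time-matched entry on the case report form. There is no added patient procedure and no change to the saturation target, device settings, primary analysis or sample size. The downside is a further secondary measure that needs cautious reading.
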